Note: Participants who complete the EoT assessments but withdraw/are withdrawn prior to completion of the end-of-study assessments will be considered "completed" and do not require replacement if they completed all prior PK/PD sampling within window and received all doses per the SoA. Participants who withdraw/are withdrawn prior to the end-of-treatment visit should have the end-of-treatment assessments performed, if possible, and will be replaced unless

3 participants in their cohort have already "completed" or are on track to "complete".

^a Visits designated "I/O" may be performed Inpatient or Outpatient at the Investigator's discretion.

^b All postdose timepoints are relative to the start of the IV infusion/time of the SC injection (ie, Time 0) except the vital signs measurements, PK and PD sample, and infusion site evaluation performed/collected at the EoI (see Table 3).

° Signed and dated IEC-approved ICF must be obtained before any study-specific screening procedures are performed.

^d If available, historical results are acceptable, and a confirmatory test is not required.

^e Female participants who claim postmenopausal status will have an FSH test to confirm status.

^f A negative drug screen is required for participant enrollment. Results from drug screens collected at timepoints prior to dosing (Days -1, 14, 21, 28) are not required to confirm a negative result prior to dosing. The drug screen results received after sampling will be noted, and if positive, the participant will be

ALXN1850-HPP-101

Protocol Amendment 5 10 Mar 2022

discontinued from the study. If negative, the results will serve as clearance to proceed with dosing for future pre-dosing days. A positive drug test result for a non-prescribed substance received at any visit will lead to discontinuation

- ^g Pregnancy test must be performed on all participants of child-bearing potential at the specified time points. Additional pregnancy tests may also be performed at any time at the Investigator's discretion.
- ^h Predose and postdose abbreviated PEs are allowed at the predose or dosing day, and on the day after dosing or 2 days after dosing, depending on when the participant is admitted and discharged.
- ⁱ If a potential participant is rescreened, these assessments do not need to be performed again unless more than 12 months will have elapsed between each test and enrollment.

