7. DISCONTINUATION OF STUDY INTERVENTION AND PARTICIPANT DISCONTINUATION/WITHDRAWAL

Stopping rules provide explicit guidance for the discontinuation of treatment cohorts and discontinuation of individual participants. The following rule sets apply to TEAEs that are assessed by the Investigator to be related to study drug (unless specified otherwise). While stopping rules provide an explicit guide for dose discontinuation, the Investigator and/or Alexion may elect to discontinue dosing at any time. Dose continuation or escalation will proceed as scheduled and the study will continue as planned provided no prespecified toxicity events occur (as determined by the SRC).

The entire study will be suspended if any severe or life-threatening treatment-emergent serious adverse events (TESAEs) occur.

Participants who do not complete the study but have been dosed should make every effort to undergo all scheduled safety, PK, and PD evaluations required by the protocol (refer to SoA, Section 1.3) in relation to the last dose they received. Alexion and site monitor will be notified as soon as possible.

If a participant withdraws consent and is unwilling to attend all scheduled procedures, every attempt will be made to encourage them to complete the ED visit at a minimum.

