7.2. Participant Discontinuation/Withdrawal from the Study

- All efforts should be made to ensure participants are willing to comply with study participation prior to conducting the screening procedures. The study staff should notify Alexion and their site monitor of all study withdrawals as soon as possible. The reason for participant discontinuation must be recorded in the source documents and eCRF.
- A participant may withdraw from the study at any time at his/her own request or may be withdrawn at any time at the discretion of the Investigator for safety, behavioral, compliance, or administrative reasons.
- At any visit, a positive drug test result for a non-prescribed substance will lead to participant discontinuation.
- A positive pregnancy test result at any time during the study will lead to participant discontinuation.
- Participants diagnosed with COVID-19 with clinical manifestations of the disease will be evaluated for potential treatment and/or study discontinuation according to the CRU's COVID-19 protocol.
- At the time of discontinuing from the study, if possible, an Early Discontinuation visit should be conducted, as shown in the SoA. See SoA (Section 1.3) for data to be collected at the time of discontinuation and follow-up and for any further evaluations that need to be completed.
- If the participant withdraws consent for disclosure of future information, Alexion may retain and continue to use any data collected before such a withdrawal of consent.
- If a participant withdraws from the study, he/she may request destruction of any samples taken and not tested, and the Investigator must document this in the site study records.
- Participants who withdraw/are withdrawn from the study following completion of EoT assessments but prior to completion of EoS assessments will be considered "completed" if all PK/PD sampling was performed within window and all doses were administered per the SoA. "Completed" participants do not need to be replaced.

Page 48 of 97	
Alexion Confidential	

- Participants who withdraw/are withdrawn from the study prior to completion of the end-of-treatment assessments should be replaced unless at least 3 participants in their cohort have already "completed" or are on track to "complete".

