Please file this letter and any IRB/EC correspondence with all copies of the protocol in the Investigator Site File and in all pertinent repositories in which the protocol is maintained. If there are any questions concerning these changes, please contact us. Applicable changes will also be captured in any future protocol amendment.

Phone:			
Email:			

Cc: eTMF

Page 2 of 5	
Alexion Confidential	

Table 1: Schedule of Activities - Study Overview for the First Participant in Each Cohort

Assessments	Screening			Treatment Period											EoT/ED Assessment	FU/ EoS Assessment							
Inpatient (I) or Outpatient (O) ^a	0	I/O	Ι	I	I/O	0	0	I/O	I	I	I/O	0	I/O	I	I	I/O	I	I	I/O	0	0	0	0
Study Day	-56 to -2	-1	1	2	2 3 5 8 14 15 16 17 19 21 22 23 28 29 30 31 36 51									65	85								
Hours postdose ^b				24	48	96	168			24	48	96			24			24	48	168			
Injection/ infusion site evaluation ^c				Х	Х		Х			Х	Х				Х			Х	Х	Х			
Hypersensitivity rxn labs (tryptase, IgE, C5b-9) ^d												← Se	e footi	note-"	X ⁿ –	→							
Chemistry, hematology, and urinalysis labs													← 2	$\langle n \rightarrow$									

^b All postdose timepoints are relative to the start of the IV infusion/time of the SC injection (ie, **T**time 0) except the **ECG**vital signs measurements, and PK/-and PD samples, and infusion site evaluation performed/collected at the EoI (see Table 3).

Error! Reference source not found. Injection/infusion site evaluations will be performed within 15 minutes (\pm 5 minutes) after injection/EoI and \pm 15 minutes of the timepoints. from Time 0h and every 15 minutes (\pm 5 minutes) until the 1st hr after the start of the injection/infusion. The rest of the timepoints have a window of \pm 15 minutes (see Table 3).

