8.2. Plasma Pharmacokinetic Concentrations

Blood samples for analysis of concentrations of ALXN1850 in plasma for each of the treatments will be collected at the following time points:

First participant within each cohort	Subsequent participants within each cohort
Day 1: pre-dose, EOI, and 2h, 6h,, and 12h	Day 1: pre-dose, EOI, and 2h, 6h,, and 12h
post dose (IV dose)	post dose (IV dose)
Day 2 (24 hours post IV dose)	Day 2 (24 hours post IV dose)
Day 3 (48 hours post IV dose)	Day 3 (48 hours post IV dose)
Day 5 (96 hours post IV dose)	Day 5 (96 hours post IV dose)
Day 8 (168 hours post IV dose)	
Day 15: pre-dose and 2h, 6h, and 12h post	Day 8: pre-dose and 2h, 6h, 8h, and 12h post
dose (SC dose 1)	dose (SC dose 1)
Day 16 (24 hours post SC dose 1)	Day 9 (24 hours post SC dose 1)
Day 17 (48 hours post SC dose 1)	Day 10 (48 hours post SC dose 1)
Day 19 (96 hours post SC dose 1)	Day 12 (96 hours post SC dose 1)
-	
Day 22: pre-dose and 2h, 6h, and 12h post	Day 15: pre-dose and 2h, 6h, and 12h post
dose (SC dose 2)	dose (SC dose 2)
Day 23 (24 hours post SC dose 2)	Day 16 (24 hours post SC dose 2)

Page 12 of 29

Day 29: pre-dose and 2h, 6h, and 12h post	Day 22: pre-dose and 2h, 6h, and 12h post
dose (SC dose 3)	dose (SC dose 3)
Day 30 (24 hours post SC dose 3)	Day 23 (24 hours post SC dose 3)
Day 31 (48 hours post SC dose 3)	Day 24 (48 hours post SC dose 3)
Day 36 (168 hours post SC dose 3)	Day 29 (168 hours post SC dose 3)
Day 51 (3 weeks post SC dose 3)	Day 43 (3 weeks post SC dose 3)
Day 65 (5 weeks post SC dose 3)	Day 57 (5 weeks post SC dose 3)
Day 85 (8 weeks post SC dose 3)	Day 78 (8 weeks post SC dose 3)

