Pharmacodynamic analysis (PPi, PLP, and PL) will be performed at below timepoint:

First participant within each cohort	Subsequent participants within each cohort
Day 1 (pre IV dose); EoI (end of infusion)	Day 1 (pre IV dose); EoI (end of infusion)
Day 2 (24 hours post IV dose)	Day 2 (24 hours post IV dose)
Day 3 (48 hours post IV dose)	Day 3 (48 hours post IV dose)
Day 5 (96 hours post IV dose)	Day 5 (96 hours post IV dose)
Day 8 (1 week post IV dose)	
Day 15 (pre SC dose 1)	Day 8 (pre SC dose 1)
Day 16 (24 hours post SC dose 1)	Day 9 (24 hours post SC dose 1)
Day 17 (48 hours post SC dose 1)	Day 10 (48 hours post SC dose 1)
Day 19 (96 hours post SC dose 1)	Day 12 (96 hours post SC dose 1)
Day 22 (pre SC dose 2)	Day 15 (pre SC dose 2)
Day 23 (24 hours post SC dose 2)	Day 16 (24 hours post SC dose 2)
Day 29 (pre SC dose 3)	Day 22 (pre SC dose 3)

Page 24 of 29

First participant within each cohort	Subsequent participants within each cohort
Day 30 (24 hours post SC dose 3)	Day 23 (24 hours post SC dose 3)
Day 31 (48 hours post SC dose 3),	Day 24 (48 hours post SC dose 3)
Day 36 (1 week post SC dose 3)	Day 29 (1 week post SC dose 3)
Day 51 (3 weeks post SC dose 3)	Day 43 (3 weeks post SC dose 3)
Day 65 (5 weeks post SC dose 3)	Day 57 (5 weeks post SC dose 3)
Day 85/ED/EoS (8 weeks post SC dose 3)	Day 78/ED/EoS (8 weeks post SC dose 3)

Relative time to dose includes:

- Baseline, 24 hours post IV dose, 48 hours post IV dose, 96 hours post IV dose, and 1 week post IV dose;
- Pre SC dose 1, 24 hours post SC dose 1, 48 hours post SC dose 1, and 96 hours post SC dose 1;
- Pre SC dose 2, 24 hours post SC dose 2;
- Pre SC dose 3, 24 hours post SC dose 3, 48 hours post SC dose 3, 1 week post SC dose 3, 3 weeks post SC dose 3, 5 weeks post SC dose 3, and 8 weeks post SC dose 3.

Summary statistics will be presented for absolute, change from baseline, and percent change from baseline for PLP, PLP/PL ratio, and PPi by cohort and relative time to dose for all participants, and will be further repeated by each ADA status (ADA negative and ADA positive, and/or pre-existing immunogenicity, treatment-emergent ADA responses, and treatment-boosted ADA responses if data permits). This summary table will be repeated including all participants up to 1 week post IV dose and subsequent participants for the remaining relative time to dose.

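### The SAP gives Early Discontinuation the nominal time of the 8-week end-of-study visit, while the protocol pairs it with end of treatment and holds it when the participant leaves; no rule maps it correctly

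*SAP*

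**What the plan says.** **SAP.** The timepoint tables for vital signs (Section 9.3), PD (Section 10), ADA/NAb (Section 11), and bone biomarkers and pyridoxic acid (Section 12) end with "Day 85/ED/EoS (8 weeks post SC dose 3" for the first participant in a cohort and "Day 78/ED/EoS (8 weeks post SC dose 3" for the others. The late PD summary rows are "3 weeks post SC dose 3, 5 weeks post SC dose 3, and 8 weeks post SC dose 3"; none is set aside for ED. The PK table in Section 8.2 uses "Day 85 (8 weeks post SC dose 3", without ED. Section 9.9 carries the combined Day 78 label for pregnancy tests, which are only listed.

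**Protocol.** In Section 1.3, Table 1, ED shares the Day 65 EoT column, and the Day 85 column carries no ED label. Protocol Administrative Change Letter #6 repeats the heading as "EoT/ED Assessment". Table 2 names only EoT in its Day 57 heading, but the note under both tables reads: "Participants who withdraw/are withdrawn prior to the end-of-treatment visit should have the end-of-treatment assessments performed, if possible". On timing, Section 7.2 says: "At the time of discontinuing from the study, if possible, an Early Discontinuation visit should be conducted, as shown in the SoA".

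**The concern.** The two documents attach ED to different visits, and the SAP's choice also fixes a time since dose. An ED visit happens whenever the participant leaves. Someone who stops after the IV dose, or after one SC injection, would hold a result labelled as taken 8 weeks after a third SC dose that was never given.

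The 8-week row is the last look off drug: whether PPi and PLP have returned towards baseline, and where ADA titer and bone markers stand. An on-drug value does not belong there. Cohorts number about five, so a single misplaced value is a visible share of the mean, and the PD tables and mean figures are repeated by ADA status, which makes the cells smaller still.

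Nothing in the SAP clearly stops this. Section 4 keeps unscheduled results out of the summary tables, but the SAP lists ED inside a scheduled timepoint. It states no visit-window rule.

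**Working it through.** **1. Reproduce the label.** Protocol Section 1.3 puts SC dose 3 on Day 29 (first participant) or Day 22 (others), and end of study (EoS) on Day 85 or Day 78.
- (85 - 29)/7 = 56/7 = 8.0 weeks
- (78 - 22)/7 = 56/7 = 8.0 weeks

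The label is right for EoS. With the EoS window of -7/+14 days, the row covers (56 - 7)/7 = 7.0 to (56 + 14)/7 = 10.0 weeks.

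**2. Test it for ED at the nominal EoT day.**
- Day 65: (65 - 29)/7 = 36/7 = 5.1 weeks. With the -3/+7 day window: 33/7 = 4.7 to 43/7 = 6.1 weeks.
- Day 57: (57 - 22)/7 = 35/7 = 5.0 weeks. With the window: 32/7 = 4.6 to 42/7 = 6.0 weeks.

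Neither range reaches 7.0 weeks, so the label is wrong for ED even at the visit with which the protocol pairs it.

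**3. Test it for an early exit.** A subsequent participant receives SC dose 1 on Day 8. An ED visit on Day 10 is 2 days after that dose, and SC dose 3 has not been given.

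As an illustration only: the Amendment 4 rationale in Protocol Section 10.9 equates the EoT visit with 5.5 half-lives. Counted from SC dose 3, that implies about 35/5.5 = 6.4 days. Under simple exponential decline, 0.5^(3/6.36) = 72% of the level remains after 3 days and 0.5^(56/6.36) = 0.2% after 56 days.

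**4. Weight and shift.** With k true 8-week values and one ED value, the ED weight is 1/(k + 1) and the row mean moves by gap/(k + 1). The values k = 3 and k = 4 follow from about 5 enrolled and at least 3 completers per cohort. The gap is the difference in percent change from baseline between the ED value and the true 8-week values. The documents give no figure for it, so 30 to 80 points is assumed.

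| Assumed gap (points) | k = 3 (weight 1/4 = 25%) | k = 4 (weight 1/5 = 20%) |
|---|---|---|
| 30 | 30/4 = 7.5 | 30/5 = 6 |
| 50 | 50/4 = 12.5 | 50/5 = 10 |
| 80 | 80/4 = 20 | 80/5 = 16 |

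With ED values kept out of the row, the shift is 0.

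**The case against.** **Pooling is not stated.** The tables carrying the ED label are collection schedules, and the separate lists of summary rows name 8 weeks without ED. A reader might infer that the SAP expressly orders ED values into the 8-week row; no sentence does. That stands. But the label gives ED that nominal time, and no other row or rule offers an alternative.

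**There are partial safeguards.** Protocol Section 7 says: "Participants who do not complete the study but have been dosed should make every effort to undergo all scheduled safety, PK, and PD evaluations", counted from the last dose received. Continued follow-up would supply properly timed values, but it does not say where the ED value goes. The PD Set could exclude a participant with too short a profile, yet SAP Section 4.4 gives no criterion. Vital signs use the Safety Set, and the Immunogenicity Analysis Set needs only one reportable ADA result after the first dose, so early dropouts can stay in both.

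**The frequency is unknown.** A reader might take the difference between 15 enrolled and 9 completers as an expected number of dropouts. The documents do not support that: being completed also requires in-window PK/PD sampling and every dose (Protocol Section 9.2), and Section 7.2 lets someone who misses a dose remain in the study. A weight above 25% would need fewer than three true 8-week values, which is below the completer target and arises only if completers also miss EoS.

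**The direction is not general.** A reader might infer a bias towards continued effect in every marker. That is plausible for PD. An early sample may precede antibody formation and so understate titer, and the documents say nothing that settles the direction for bone markers.

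**The row decides little.** No decision rule uses it, the Amendment 4 rationale treats EoT as the last critical PK/PD timepoint, medians and listings are also planned, and a dropout between EoT and EoS would distort little. All of this stands and limits the importance.

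**Conclusion.** The point holds as a contradiction between the SAP's label and the protocol, together with a missing mapping rule. It should be settled before programming.

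Its reach is the 8-week descriptive row for vital signs, PD, ADA titer, bone biomarkers and pyridoxic acid. The effect is conditional: a participant must drop out, have an ED sample taken, and remain in the relevant analysis set. If so, and if the label is followed, one value carries 20-25% of a row of 4-5. For PD, the shift of about 6-20 points rests entirely on the assumed 30-80 point gap. For ADA titer and bone markers no direction can be given.

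The TEAE/TESAE endpoint, PK concentrations, and ADA/NAb incidence, which counts a positive result at any time, are not affected.

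A reader might also count the late laboratory and ECG rows as part of the ED problem. They are mainly a separate gap. SAP Section 9.2 schedules EoT laboratory tests, but its summary rows stop at 1 week after SC dose 3. Section 9.5 has an 8-week ECG row although the last scheduled ECG is at EoT.

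**What to change.** 1. Delete ED from the Day 85 and Day 78 timepoint labels in SAP Sections 9.3, 10, 11 and 12, and align the Day 78 label in Section 9.9.
2. Add one rule: an ED result enters a nominal summary row only if the dose number and the actual time since the last dose both match that row. Otherwise it appears in listings and individual plots, or in a separate ED row, and still counts towards any-time outcomes such as worst grade and ADA ever positive. Many dosing-phase visits have no permitted day window in the protocol, so the rule must say what counts as a match. A separate ED row would usually hold few values, so listings and plots may suffice.
3. Separately, align the late summary rows with the scheduled EoT visit: add an EoT row for laboratory tests in Section 9.2 and replace the 8-week ECG row in Section 9.5.

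The cost is SAP wording and a visit-mapping step in programming. No new data and no change to study conduct are needed.
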